All Other Drug-Related Toxicity²	3 or Severe	Toxicity resolves to Grade 0-1	Toxicity does not resolve within 12 weeks of last dose or inability to reduce corticosteroid to 10 mg or less of prednisone or equivalent per day within 12 weeks.
	4	Permanently discontinue	Permanently discontinue

Note: Permanently discontinue for any severe or Grade 3 drug-related AE that recurs or any life-threatening event.
¹ For participants with liver metastasis who begin treatment with Grade 2 AST or ALT, if AST or ALT increases by greater than or equal to 50% relative to baseline and lasts for at least 1 week then participants should be discontinued.
² Participants with intolerable or persistent Grade 2 drug-related AE may hold study medication at physician discretion. Permanently discontinue study drug for persistent Grade 2 adverse reactions for which treatment with study drug has been held, that do not recover to Grade 0-1 within 12 weeks of the last dose.

Table 8: Dose modification guidelines for drug-related adverse events

If the toxicity does not resolve to Grade 0-1 within 12 weeks after last infusion, trial treatment should be discontinued at the discretion of the investigator. Participants with a laboratory adverse event still at Grade 2 after 12 weeks may continue treatment in the trial only if asymptomatic and controlled. For information on the management of adverse events, see section 7.

Participants who experience a recurrence of the same severe or life-threatening event at the same grade or greater with re-challenge of pembrolizumab should be discontinued from trial treatment.

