Grades 3 or 4 Grade 3: Prolonged (i.e., not rapidly responsive to symptomatic medication and/or brief interruption of infusion); recurrence of symptoms following initial improvement; hospitalisation indicated for other clinical sequelae (e.g., renal impairment, pulmonary infiltrates) Grade 4: Life-threatening; pressor or ventilatory support indicated	
Stop Infusion.
 
Additional appropriate medical therapy may include but is not limited to:
 
 • IV fluids • Antihistamines • NSAIDS • Acetaminophen • Narcotics • Oxygen • Pressors • Corticosteroids • Epinephrine 
Increase monitoring of vital signs as medically indicated until the participant is deemed medically stable in the opinion of the investigator. Hospitalisation may be indicated.
 
Participant is permanently discontinued from further trial treatment administration.
	
No subsequent dosing

Appropriate resuscitation equipment should be available in the room and a physician readily available during the period of drug administration. For further information, please refer to the Common Terminology Criteria for Adverse Events v4.0 (CTCAE) at http://ctep.cancer.gov
		

Table 8: below shows treatment guidelines for participants who experience an infusion reaction associated with administration of pembrolizumab.

6.5.2. Supportive Care Guidelines for Immune-related Adverse Event (irAE) and Immune-related Events of Clinical Interest (irECI)

Immune-related Adverse events (IrAEs) may be defined as an adverse event of unknown etiology, associated with drug exposure and is consistent with an immune phenomenon. IrAEs may be predicted based on the

nature of the pembrolizumab compound, its mechanism of action, and reported experience with immunotherapies that have a similar mechanism of action. Special attention should be paid to AEs that may be suggestive of potential irAEs. An irAE can occur shortly after the first dose or several months after the last dose of treatment.

If an irAE is suspected, efforts should be made to rule out neoplastic, infectious, metabolic, toxin or other etiologic causes prior to labeling an adverse event as an irAE. Participants who develop a Grade 2 or higher irAE should be discussed immediately with the CI/designee.

Recommendations to managing irAEs not detailed elsewhere in the protocol;

irAE	Withhold/Discontinue pembrolizumab?	Supportive Care
Grade 1	No action	Provide symptomatic treatment

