Grade 2	May withhold pembrolizumab	Consider systemic corticosteroids in addition to appropriate symptomatic treatment. Steroid taper should be considered once symptoms improve to Grade 1 or less and tapered over at least 4 weeks.
Grade 3 and Grade 4	Withhold pembrolizumab Discontinue if unable to reduce corticosteroid dose to < 10 mg per day prednisone equivalent within 12 weeks of toxicity	Systemic corticosteroids are indicated in addition to appropriate symptomatic treatment. May utilize 1 to 2 mg/kg prednisone or equivalent per day. Steroid taper should be considered once symptoms improve to Grade 1 or less and tapered over at least 4 weeks.
Please Note: If an irAE does not resolve or improve to ≤ Grade 1 within 12 weeks after last administration of pembrolizumab, study therapy discontinuation should be considered after discussion with a Merck Clinical Director via the RM-CTU trial manager..		

Table 9: General Approach to Handling irAEs

Details for managing specific irAEs are summarised below:

Immune-mediated pneumonitis

Monitor participants for signs and symptoms of pneumonitis. If pneumonitis is suspected, evaluate with radiographic imaging. Exclude other causes of pneumonitis, and manage treatment in accordance with the guidelines above. Administer corticosteroids, withhold pembrolizumab for moderate (Grade 2) pneumonitis, and permanently discontinue pembrolizumab for severe (Grade 3) or life-threatening (Grade 4) pneumonitis.

Immune-mediated colitis

Monitor participants for signs and symptoms of colitis. Exclude other causes of colitis, and manage treatment in accordance with the guidelines above. Administer corticosteroids, withhold pembrolizumab for moderate (Grade 2) or severe (Grade 3) colitis, and permanently discontinue pembrolizumab for life-threatening (Grade 4) colitis.

Immune-mediated hepatitis

Monitor participants for changes in liver function (at the start of treatment, periodically during treatment and as indicated based on clinical evaluation) and symptoms of hepatitis. Exclude other causes of hepatitis, and manage treatment in accordance with the guidelines above. Administer corticosteroids and, based on severity of liver enzyme elevations, withhold or discontinue pembrolizumab.

Immune-mediated nephritis

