7.2.1.1. Determining AE Severity and Grade

AE severity and grade will be evaluated according to the NCI Common Terminology for Adverse Events (CTCAE), version 4.0 and LENT SOMA radiation toxicity grading system. Any adverse event which changes CTCAE grade over the course of a given episode should be closed at the date the severity changed and a new AE recorded on the AE e-case report forms from that date at the new severity.

Grade 1	Mild; asymptomatic or mild symptoms; clinical or diagnostic observations only; intervention not indicated.
Grade 2	Moderate; minimal, local or non-invasive intervention indicated; limiting age-appropriate instrumental ADL.
Grade 3	Severe or medically significant but not immediately life-threatening; hospitalisation or prolongation or hospitalisation indicated; disabling; limiting self-care ADL.
Grade 4	Life threatening consequences; urgent intervention indicated.
Grade 5	Death related to AE

Table 11: AE severity

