	Grade 3	
 Report as ECI within 24 hours Withhold Pembrolizumab Consider dermatology consultation and biopsy for diagnosis. 	
 1mg/kg/day prednisone or equivalent or dexamethasone 4mg 4xday. Symptoms grade 1 or less initiate steroid taper for no less than 4 weeks. Permanently discontinue pembrolizumab if dose cannot be reduced to prednisone 10mg or less or equivalent per day within 12 weeks.
	Grade 4	
 Report as ECI within 24 hours Discontinue pembrolizumab Dermatology consultation Consider biopsy for diagnosis & clinical photographs 	
 Initiate steroids starting with 1-2mg/kg prednisone or equivalent.. Symptoms grade 1 or less, initiate steroid taper for no less than 4 weeks.
Other: Myocarditis Pericarditis Pancreatitis Any additional Grade 3 or higher event which the physician considers to be immune related	Grade 2 or Grade 1 that do not improve with symptomatic treatment.	
 Report as ECI within 24 hours Withhold Pembrolizumab Consider biopsy for confirmation of diagnosis. 	
 Systemic corticosteroids may be indicated. If so: Treat with systemic corticosteroids at a dose of 1 to 2 mg/kg prednisone or equivalent once per day. When symptoms improve to Grade 1 or less, steroid taper should be started and continued over no less than 4 weeks. Permanently discontinue for inability to reduce corticosteroid dose to 10 mg or less of prednisone or equivalent per day within 12 weeks. Otherwise, pembrolizumab treatment may be restarted and the dose modified as specified in the protocol
	Grade 3	
 Report as ECI within 24 hours Withhold Pembrolizumab 	
 Treat with systemic corticosteroids at a dose of 1 to 2 mg/kg prednisone or equivalent once per day. When symptoms improve to Grade 1 or less, steroid taper should be started and continued over no less than 4 weeks. Permanently discontinue for inability to reduce corticosteroid dose to 10 mg or less of prednisone or equivalent per day within 12 weeks. Otherwise, pembrolizumab treatment may be restarted and the dose modified as specified in the protocol

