	Grade 4	
 Report as ECI within 24 hours Discontinue Pembrolizumab 	
 Treat with systemic corticosteroids at a dose of 1 to 2 mg/kg prednisone or equivalent once per day.

To be left blank

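### Table 9 (6.5.2) only withholds pembrolizumab for a non-endocrine Grade 4 immune-related event that Table 8 and Appendix 4 say should end treatment, and no sentence expressly ranks the rules

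*Combined protocol and SAP*

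**What the plan says.** Two table numbers are used twice. Here Table 8 is the dose-modification table in 6.3.8, not the infusion-reaction table. Table 9 is the general approach to irAEs in 6.5.2, not the list of events of clinical interest in 7.4.

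- **Table 9, 6.5.2.** Its scope is "Recommendations to managing irAEs not detailed elsewhere in the protocol". Grades 3 and 4 share one row: "Withhold pembrolizumab Discontinue if unable to reduce corticosteroid dose to < 10 mg per day prednisone equivalent within 12 weeks of toxicity". A note adds that if an irAE has not come down to Grade 1 or below within 12 weeks of the last dose, stopping should be considered after a discussion with the drug supplier's clinical director, arranged through the trials unit.
- **Table 8, 6.3.8.** The catch-all row for other drug-related toxicity holds treatment at Grade 3 and stops it permanently at Grade 4. The note reads: "Permanently discontinue for any severe or Grade 3 drug-related AE that recurs or any life-threatening event". Section 7.2.1.1 defines Grade 4 as "Life threatening consequences; urgent intervention indicated".
- **Appendix 4, Other.** This block includes "Any additional Grade 3 or higher event which the physician considers to be immune related". Its Grade 4 action is "Discontinue Pembrolizumab".
- **Closing paragraph of 6.5.2.** Immune-related events of clinical interest (irECIs) are those listed in 7.4. Once judged drug-associated, they are referred to Appendix 4 for management. The last entry of the 7.4 list is a catch-all for other immune-related events, and it names Grade 3 only.

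**The concern.** The same Grade 4 event can fall under three catch-all rules that do not agree. Two end treatment. The third suspends it and names a single stopping condition, failure to taper steroids.

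The case that matters is a Grade 4 irAE that settles and is off high-dose steroids within 12 weeks. Table 9's stopping condition is then not met, and its 12-week note does not apply either, because the event has resolved. A site working from that table alone could regard re-dosing as open after a life-threatening event. What is at stake is patient safety and consistent conduct across 15 to 24 sites.

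**Working it through.** No arithmetic beyond counting applies. The check sets the rules side by side.

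**1. Do the scopes overlap?** Yes. Section 6.5.2 describes an irAE as "associated with drug exposure and is consistent with an immune phenomenon", so an irAE is also a drug-related toxicity and falls within Table 8's catch-all row. It is also immune related, so at Grade 3 or above it fits the Other block of Appendix 4.

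**2. What does each rule say at Grade 4 for an event with no organ-specific entry?**
- Table 9: withhold; stop if steroids cannot be tapered in 12 weeks.
- Table 8, catch-all row: permanently discontinue.
- Table 8, note: permanently discontinue for a life-threatening event, which is how 7.2.1.1 defines Grade 4.
- Appendix 4, Other: discontinue (without the word permanently).

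**3. Which rule is out of line?**
- Table 8 has 9 rows that reach Grade 4. Those that stop are colitis, liver tests, hyperthyroidism, infusion reaction, pneumonitis, renal and the catch-all: 7. Those that hold are type 1 diabetes/hyperglycaemia and hypophysitis: 2. Removing hyperthyroidism leaves 7 − 1 = 6 non-endocrine rows, all of which stop. This count reads the unlabelled Grade 3-4 row printed before the renal Grade 2 row as renal. Hypothyroidism carries no grade and is left out.
- Appendix 4 has 13 blocks with a Grade 4 rule. Of these, 11 discontinue: pneumonitis, colitis, hyperthyroidism, haematologic, hepatic, neurologic, ocular, renal, two skin blocks and Other. The remaining 2 are hypophysitis/other endocrinopathy and type 1 diabetes/hyperglycaemia. Non-endocrine blocks: 11 − 1 (hyperthyroidism) = 10, all of which discontinue. Grade 2-4 hypothyroidism shares the thyroid block and may continue on replacement.
- The text of 6.5.2 itself stops treatment for Grade 4 pneumonitis, colitis and nephritis.

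Table 9 is therefore the only table row found that withholds for a non-endocrine Grade 4 irAE.

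**4. Does anything settle the order?** Two sentences point to the stricter rule: Table 9's scope line, and the referral of drug-associated irECIs to Appendix 4. Two gaps remain. The 7.4 catch-all stops at Grade 3 in its wording while Appendix 4 extends upward, and no sentence says that Table 8 or Appendix 4 overrides Table 9. The last sentence of 6.3.8, on a severe or life-threatening event recurring at re-challenge, fits the endocrine allowances but does not exclude the Table 9 reading.

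**5. Steroid threshold.** Table 9 requires a dose below 10 mg/day; Table 8 and Appendix 4 accept 10 mg or less. They differ only at exactly 10 mg/day.

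**6. Secondary point: the 12-week stop.** Seven Table 8 rows list non-resolution within 12 weeks as a ground for discontinuation, and footnote 2 makes the stop permanent for held, persistent Grade 2 reactions. The paragraph under the table leaves the stop to the investigator's discretion. All 7 rows still ask for Grade 0-1 in the restart column, although hypophysitis also allows treatment to continue during endocrine replacement.

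**The case against.** The strongest reply is that Table 9 yields by its own terms. It covers only irAEs that the protocol does not deal with elsewhere. Since Table 8 and Appendix 4 each have a catch-all, the Grade 4 half of the row may apply to nothing. Section 6.5.2 then closes by sending drug-associated irECIs to Appendix 4 and says that treatment of symptomatic ones must stop at once. Section 6.3.8 is the binding dose-modification section, while Table 9 sits among supportive-care guidelines. Table 9 contains no restart wording, so withholding may be meant only as the immediate action. There is also a human check: "Participants who develop a Grade 2 or higher irAE should be discussed immediately with the CI/designee".

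Most of this stands, and it limits the point. A reader might infer that the protocol authorises a restart after Grade 4 irAEs, or that nothing directs a site to the stricter rule. The documents support neither inference. What remains is narrower. If the Grade 4 half of the row is redundant, it is a misleading instruction in the table sites are likely to consult. If it is not, it conflicts with three other statements. The discussion with the chief investigator is a real safeguard, but the text does not say which rule that discussion should apply.

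**Conclusion.** The inconsistency is real and minor. For a non-endocrine Grade 4 irAE without an organ-specific entry, Table 9 gives a weaker instruction than Table 8, its note and Appendix 4, and precedence has to be inferred. Harm would require a site to rely on Table 9 alone and not be corrected in discussion with the chief investigator. The documents give no basis for estimating how often that would happen.

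Two further inferences should be resisted. Table 9 is not shown to be the outlier at Grade 3: Table 8's catch-all row also holds, and Appendix 4's Other block also withholds and names only taper failure as a stop. Nor does the discretionary sentence under Table 8 clearly permit re-dosing with unresolved non-laboratory toxicity. That conflict is about whether stopping is mandatory.

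The primary endpoint, sample size and analysis are unaffected.

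**What to change.** **Main change.**
- Split the Table 9 row. Make Grade 4 *Permanently discontinue*, except for the endocrine allowances in Table 8 and the 6.5.2 allowance for a resolved Grade 3-4 endocrinopathy controlled on hormone replacement. Leave Grade 3 as *Withhold*.
- Align the steroid threshold to 10 mg or less.
- Extend the 7.4 catch-all to Grade 3 or higher, matching Appendix 4.

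**Optional change.** If the 12-week stop below Table 8 is to be mandatory, removing the discretion is not enough. The sentence must except asymptomatic, controlled Grade 2 laboratory events, which the protocol already allows to continue, and endocrinopathies controlled on hormone replacement. Otherwise it would clash with the hypothyroidism and hypophysitis allowances. The Table 9 note, which only asks that stopping be considered at 12 weeks, must be brought into line as well.

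**Cost.** The main change rewords one table row and one list entry. The optional change adds one sentence and one note. Because a treatment-stopping rule changes, it goes through the amendment route in 10.7. No visits, tests, patients or analyses are added.

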6.5.3. Supportive Care Guidelines for Pneumonitis

Participants with symptomatic pneumonitis should immediately stop receiving pembrolizumab and have an evaluation. The evaluation may include bronchoscopy and pulmonary function tests to rule out other causes such as infection. If the participant is determined to have study drug associated pneumonitis, the suggested treatment plan is detailed in Table 10.

Study drug associated pneumonitis	Withhold/Discontinue pembrolizumab?	Supportive Care
Grade 1 (asymptomatic)	No action	Intervention not indicated
Grade 2	Withhold pembrolizumab, may return to treatment if improves to Grade 1 or resolves within 12 weeks. Second episode of pneumonitis – discontinue pembrolizumab if upon re-challenge the participant develops a second episode of Grade 2 or higher pneumonitis.	Consider pulmonary consultation with bronchoscopy and biopsy/BAL. Conduct an in person evaluation approximately twice per week Consider frequent Chest X-ray as part of monitoring Treat with systemic corticosteroids at a dose of 1 to 2 mg/kg/day prednisone or equivalent. When symptoms improve to Grade 1 or less, steroid taper should be started and continued over no less than 4 weeks. Consider antibiotics
Grade 3 and Grade 4	Discontinue pembrolizumab	Hospitalise participant

		
Bronchoscopy with biopsy and/or BAL is recommended.
 
Immediately treat with intravenous steroids (methylprednisolone 125 mg IV). When symptoms improve to Grade 1 or less, a high dose oral steroid (prednisone 1 to 2 mg/kg once per day or dexamethasone 4 mg every 4 hours) taper should be started and continued over no less than 4 weeks.
 
If IV steroids followed by high dose oral steroids does not reduce initial symptoms within 48 to 72 hours, treat with additional anti-inflammatory measures. Discontinue additional anti-inflammatory measures upon symptom relief and initiate a prolonged steroid taper over 45 to 60 days. If symptoms worsen during steroid reduction, initiate a re-tapering of steroids starting at a higher dose of 80 or 100mg followed by a more prolonged taper and administer additional anti-inflammatory measures, as needed. Add prophylactic antibiotics for opportunistic infections. The use of infliximab may be indicated as appropriate.

--	--	--

Table 10: Recommended Approach to Handling Pneumonitis

For Grade 2 pneumonitis that improves to \leq Grade 1 within 12 weeks, the following rules should apply:

- First episode of pneumonitis
 - May increase dosing interval by one week in subsequent cycles
- Second episode of pneumonitis
 - Permanently discontinue pembrolizumab if upon re-challenge participant develops pneumonitis \geq Grade 2

6.6. Diet/Activity/Other Considerations

6.6.1. Diet

Participants should maintain a normal diet unless modifications are required to manage an AE such as diarrhoea, nausea or vomiting.

6.6.2. Contraception

Pembrolizumab may have adverse effects on a foetus in utero. Furthermore, it is not known if pembrolizumab has transient adverse effects on the composition of sperm. Non-pregnant, non-breast-feeding women may be enrolled if they are willing to use 2 methods of birth control or are considered highly unlikely to conceive. Highly unlikely to conceive is defined as 1) surgically sterilized, or 2) postmenopausal (a woman who is ≥ 45 years of age and has not had menses for greater than 1 year will be considered postmenopausal), or 3) not heterosexually active for the duration of the study. The two birth control methods can be either, two barrier

methods or a barrier method plus a hormonal method to prevent pregnancy. Participants should start using birth control from screening throughout the study period up to 120 days after the last dose of study therapy. Male participants with partners of child bearing potential will also be required to agree to use an adequate method of contraception starting with the first dose of study therapy through 120 days after the last dose of study therapy.

The following are considered adequate barrier methods of contraception: diaphragm, condom (by the partner), copper intrauterine device, sponge, or spermicide. Appropriate hormonal contraceptives will include any registered and marketed contraceptive agent that contains an oestrogen and/or a progestational agent (including oral, subcutaneous, intrauterine, or intramuscular agents).

Participants should be informed that taking the study medication may involve unknown risks to the foetus (unborn baby) if pregnancy were to occur during the study. In order to participate in the study they must adhere to the contraception requirement (described above) for the duration of the study and during the safety follow-up period. If there is any question that a participant will not reliably comply with the requirements for contraception, that participant should not be entered into the study.

6.6.3. Use in Pregnancy

If a participant inadvertently becomes pregnant while on treatment with pembrolizumab, the participant will immediately be removed from the study. The site will contact the participant at least monthly and document the participant's status until the pregnancy has been completed or terminated. If the outcome of the pregnancy is a serious adverse experience (e.g., death, abortion, congenital anomaly, or other disabling or life-threatening complication to the mother or newborn) this will be reported to RM-CTU without delay and **within 24 hours of becoming aware of the event to the Sponsor**. The study investigator will make every effort to obtain permission to follow the outcome of the pregnancy and report the condition of the foetus or newborn to the RM-CTU. If a male patient impregnates his female partner the study personnel at the site must be informed immediately and the pregnancy reported to RM-CTU and followed as described above and in Section 7.

